6.4 Authorized associate procedures and treatment

All medication which is considered necessary for the patient's welfare, and which is not expected to interfere with the evaluation of the study drug, may be given at the discretion of the Principal Investigator. All concomitant medications (including start/stop dates, dose frequency, route of administration and indication) must be recorded in the patient's source documentation, as well as in the appropriate pages of the e-CRF.

6.4.1 Other treatments/procedures

Permitted concomitant medications:

- Atropine
- Anti-emetics
- Alpha hydroxyl acids, keratolytic, non urea creams
- Topical corticoids
- Antihistaminics
- Contrast agent
- Treatment with non-conventional therapies (for example homeopathy, vitamins or acupuncture), and vitamin/mineral supplements is acceptable provided that they do not interfere with the study endpoints, in the opinion of the Investigator.

- Bisphosphonates
- G-CSF and other hematopoietic growth factors may be used during the study in the management of acute toxicity such as febrile neutropenia when clinically indicated or at the discretion of the investigator.
- Patients taking chronic erythropoietin are permitted.

CYP isoform-selective substrates

In vitro data indicate that regorafenib is a competitive inhibitor of the cytochromes CYP2C8 (K_i value of 0.6 micromolar), CYP2C9 (K_i value of 4.7 micromolar), CYP2B6 (K_i value of 5.2 micromolar) at concentrations which are achieved *in vivo* at steady state (peak plasma concentration of 8.1 micromolar). The *in vitro* inhibitory potency towards CYP3A4 (K_i value of 11.1 micromolar) and CYP2C19 (K_i value of 16.4 micromolar) was less pronounced.

A clinical probe substrate study was performed to evaluate the effect of 14 days of dosing with 160 mg regorafenib on the pharmacokinetics of probe substrates of CYP2C8 (rosiglitazone) CYP2C9 (S-warfarin), CYP 2C19 (omeprazole) and CYP3A4 (midazolam).

Pharmacokinetic data indicate that regorafenib may be given concomitantly with substrates of CYP2C8, CYP2C9, CYP3A4, and CYP2C19 without a clinically meaningful drug interaction.

 Clinical data indicate that regorafenib has no effect on digoxin pharmacokinetics, therefore can be given concomitantly with p-glycoprotein substrates, such as digoxin, without a clinically meaningful drug interaction

6.5 Non permitted treatment

Inhibitors of CYP3A4 and UGT1A1/UGT1A9/inducers of CYP3A4

In vitro data indicate that regorafenib is metabolized by cytochrome CYP3A4 and uridine diphosphate glucuronosyl transferase UGT1A9.

Administration of ketoconazole (400 mg for 18 days), a strong CYP3A4 inhibitor, with a single dose of regorafenib (160 mg on day 5) resulted in an increase in mean exposure (AUC) of regorafenib of approximately 33%, and a decrease in mean exposure of the active metabolites, M-2 (N-oxide) and M-5 (N-oxide and N-desmethyl), of approximately 90%. It is

recommended to avoid concomitant use of strong inhibitors of CYP3A4 activity (e.g. clarithromycin, grapefruit juice, itraconazole, ketoconazole, posaconazole, telithromycin and voriconazole) as their influence on the steady-state exposure of regorafenib and its metabolites has not been studied.

Co-administration of a strong UGT1A9 inhibitor (e.g. mefenamic acid, diflunisal, and niflumic acid) during regorafenib treatment should be avoided, as their influence on the steady-state exposure of regorafenib and its metabolites has not been studied.

Administration of rifampicin (600 mg for 9 days), a strong CYP3A4 inducer, with a single dose of regorafenib (160 mg on day 7) resulted in a reduction in AUC of regorafenib of approximately 50%, a 3- to 4-fold increase in mean exposure of the active metabolite M-5, and no change in exposure of active metabolite M-2. Other strong CYP3A4 inducers (e.g. phenytoin, carbamazepine, phenobarbital and St. John's wort) may also increase metabolism of regorafenib. Strong inducers of CYP3A4 should be avoided, or selection of an alternate concomitant medicinal product, with no or minimal potential to induce CYP3A4 should be considered.

UGT1A1 and UGT1A9 substrates

In vitro data indicate that regorafenib as well as its active metabolite M-2 inhibit glucuronidation mediated by UGT1A1 and UGT1A9 whereas M-5 only inhibits UGT1A1 at concentrations which are achieved *in vivo* at steady state. This indicates that co-administration of regorafenib may increase systemic exposure to UGT1A1 and UGT1A9 substrates.

Breast cancer resistance protein (BCRP) and P-glycoprotein substrates

Administration of regorafenib (160 mg for 14 days) prior to administration of a single dose of rosuvastatin (5 mg), a BCRP substrate, resulted in a 3.8-fold increase in mean exposure (AUC) of rosuvastatin and a 4.6-fold increase in C_{max}.

This indicates that co-administration of regorafenib may increase the plasma concentrations of other concomitant BCRP substrates (e.g. methotrexate, fluvastatin, atorvastatin).

Inhibitors of P-glycoprotein and BCRP/Inducers of P-glycoprotein and BCRP

In vitro studies indicate that the active metabolites M-2 and M-5 are substrates for P-glycoprotein and BCRP. Inhibitors and inducers of BCRP and P-glycoprotein may interfere with the exposure of M-2 and M-5. The clinical significance of these findings is unknown.

Antibiotics

The concentration-time profile indicates that regorafenib and its metabolites may undergo enterohepatic circulation (see section 5.2). Co-administration with neomycin, a poorly absorbed antimicrobial agent used for eradicating the gastrointestinal microflora (which may interfere with the enterohepatic circulation of regorafenib) had no effect on the regorafenib exposure, but there was an approximately 80% decrease in the exposure of the active metabolites M-2 and M-5 which showed *in vitro* and *in vivo* comparable pharmacological activity as regorafenib. The clinical significance of this neomycin interaction is unknown, but may result in a decreased efficacy of regorafenib. Pharmacokinetic interactions of other antibiotics have not been studied.

Bile salt-sequestering agents

Regorafenib, M-2 and M-5 are likely to undergo enterohepatic circulation. Bile salt-sequestering agents such as cholestyramine and cholestagel may interact with regorafenib by forming insoluble complexes which may impact absorption (or reabsorption), thus resulting in potentially decreased exposure. The clinical significance of these potential interactions is unknown, but may result in a decreased efficacy of regorafenib.

- -Systemic anticancer therapy including cytotoxic therapy, signal transduction inhibitors, immunotherapy, hormonal therapy and experimental or approved therapies during this trial or within 30 days before starting to receive study medication.
- -Bone marrow transplant or stem cell rescue.
- -Prior radiation and concomitant palliative radiation therapy is allowed if the target lesion(s) are not included within the radiation field and no more than 10% of the bone marrow is irradiated.
- -Use of biologic response modifiers, such as granulocyte colony stimulating factor (GCSF), within 3 weeks of study entry.
- -Herbal medicine and grapefruit juice
- -Yellow fever vaccine: Risk of fatal generalized vaccine disease
- -Live attenuated vaccines: Risk of generalized vaccine disease, possibly fatal. Concomitant administration during treatment with irinotecan and for 3 months after discontinuation of

chemotherapy is contraindicated. Killed or inactivated vaccines can be administered, however the response to these vaccines can be decreased.

-Immunosuppressive agents (eg ciclosporin, tacrolimus): Excessive immunosuppression with risk of lymphoproliferation.

-Neuromuscular blocking agents: the interaction between irinotecan and neuromuscular blocking agents cannot be ruled out. Due to the anticholinesterase activity of irinotecan, drugs with anticholinesterase activity can prolong the neuromuscular blocking effects of suxamethonium and the neuromuscular blockade of non-depolarizing agents can be antagonized.

-Antivitamin K such as warfarin, phencoumarone etc.

7. Ancillary Studies

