- 28. Unresolved toxicity higher than CTCAE (V5.0) Grade 1 attributed to any prior therapy/procedure excluding alopecia, hypothyroidism and oxaliplatin induced neurotoxicity ≤ Grade 2
- 29. Concomitant participation or participation within the last 30 days in another clinical trial
- 30. Systemic anticancer therapy during this trial or within 4 weeks before randomization
- 31. Concomitant intake of St. John's wort
- 32. Live attenuated vaccines are prohibited 10 days before the treatment, during the treatment and 6 months after the termination of treatment
- 33. History of gastrointestinal fistula or perforation
- 34. Previous or concurrent cancer that is distinct in primary site or histology from colorectal cancer within 5 years prior to study inclusion, except for curatively treated cervical cancer in situ, non-melanoma skin cancer and bladder tumors [Ta (non invasive tumor), Tis (carcinoma superficial in situ and T1 (lamina propria invasion)

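### Live attenuated vaccines are barred until 6 months after treatment in criterion 32, but section 6.5 states only 3 months, counted from the end of chemotherapy

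*Combined protocol and SAP*

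**What the plan says.** Three places in the combined protocol and SAP deal with live attenuated vaccines.

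- **Synopsis, exclusion criterion 32, and section 4.3, non-inclusion criterion 32** (same wording): "Live attenuated vaccines are prohibited 10 days before the treatment, during the treatment and 6 months after the termination of treatment". Neither names an arm or a drug.
- **Section 6.5, Non permitted treatment**, gives the reason first: "Live attenuated vaccines: Risk of generalized vaccine disease, possibly fatal". It then sets the period: "Concomitant administration during treatment with irinotecan and for 3 months after discontinuation of" chemotherapy is contraindicated. Killed or inactivated vaccines are allowed.

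Section 6.5 also has a separate entry for yellow fever vaccine, which carries no time limit. Irinotecan is given in arm A only (section 6.1).

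**The concern.** One prohibition has two end dates, and they differ in length, in starting event and in the drug they refer to. A site that relied on section 6.5 alone could give a live vaccine at a time when criterion 32 still forbids it. The protocol rates the harm as possibly lethal, so the mismatch bears on patient safety as well as on tidiness.

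The protocol has little that would reveal such an event. Concomitant medications are last collected at the 30-day safety visit. After that, follow-up records only vital status and anti-cancer medications (sections 5.1 and 5.5). Routine adverse event collection also stops at 30 days (section 10.1.2), and a later serious event is notifiable only if the investigator judges it related to the investigational product (section 10.2.4.1). In the disputed window the written instruction is therefore the main safeguard.

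**Working it through.** There is no stated figure to reproduce. The check is a comparison of the texts and a subtraction.

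| Item | Criterion 32 (synopsis, section 4.3) | Section 6.5 |
|---|---|---|
| Before treatment | 10 days | not stated |
| During | treatment, no drug named | irinotecan treatment |
| After | 6 months | 3 months |
| Clock starts at | end of treatment | end of chemotherapy |
| Regorafenib alone (arm B) | 6 months | no post-treatment period |

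**Arm A, both drugs stopped together.** The two clocks start at the same moment, so the end dates differ by 6 − 3 = 3 months. From month 3 to month 6 the patient is covered by criterion 32 and is outside the period in section 6.5.

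**Arm A, drugs stopped at different times.** Let T_I and T_R be the dates on which irinotecan and regorafenib stop, in months. Assume that chemotherapy in section 6.5 means irinotecan, and that treatment in criterion 32 ends when the later drug stops.

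- End of the ban under criterion 32: max(T_I, T_R) + 6
- End of the period in section 6.5: T_I + 3
- Difference: 3 + max(T_R − T_I, 0)

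On this reading the gap is never shorter than 3 months. At the end of a complete course on the section 6.1 schedule (irinotecan on day 1, regorafenib on days 2 to 8, or day 15 and days 16 to 22), T_R − T_I is 8 − 1 = 22 − 15 = 7 days, so the gap is 3 months and 7 days.

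Criterion 32 does not say which drug starts its clock. If it ran from whichever drug stopped first, and regorafenib stopped d months before irinotecan, the gap would be (T_I − d + 6) − (T_I + 3) = 3 − d months. It would vanish only at d = 3.

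**Arm B.** Criterion 32 gives 6 months after treatment. Section 6.5 lists live vaccines without limiting the entry to arm A, but the only post-treatment period it states is tied to irinotecan.

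**How many patients.** Section 9.1 plans 2 × 39 = 78 patients, so 39 in arm A is a ceiling. The affected number must be smaller: those alive more than 3 months after stopping for whom a live vaccine is considered. The assumed median survivals of 7 and 15 months run from randomization, not from the end of treatment. The documents give no expected treatment duration and no rate of live-vaccine use, so no estimate can be made.

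**The case against.** The strongest defence is that the texts differ without colliding. Section 6.5 places live vaccines under non-permitted treatment and nowhere says that they become allowed after 3 months. The passage can be read as a drug-specific warning beneath a general trial rule, and someone who observed the longer period would breach neither. Part of this stands: a reader might infer that section 6.5 authorizes vaccination from month 4, and it does not say so. But the defence works only for someone who reads both places, and nothing in section 6.5 points to criterion 32 or says that a longer rule applies.

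A second objection is reach. A reader might infer that every arm A patient faces conflicting instructions. The documents do not support that: these are patients whose standard therapies have failed, some will not live 3 months past their last dose, and for others no live vaccine will be considered. This stands and limits the size of the point.

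A third is that site staff may not be managing vaccination by then, since follow-up may be by telephone. The documents do not show which section staff would consult at that time, so the point should not rest on any claim about it. The texts remain inconsistent whichever is consulted.

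Finally, a reader might infer that section 6.5 leaves arm B out altogether. That goes too far: the entry is not restricted by arm, and only its stated period is specific to irinotecan.

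**Conclusion.** The inconsistency is real and should be corrected. It is a conflict between passages, not a choice of design. Criterion 32 and section 6.5 give post-treatment periods of 6 and 3 months, which leaves a 3-month difference for an arm A patient who stops both drugs together and survives into it. They also differ on the starting event, on regorafenib alone and on the 10 days before treatment.

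The 3-month figure rests on reading chemotherapy as irinotecan and on the two clocks starting together. The number of patients affected is not known. A reader might take the risk wording to mean that harm is likely, or that the trial's result is in doubt; the documents support neither. The primary endpoint, randomization, sample size and analysis are untouched. What carries the point is the severity that the protocol itself assigns to the risk, and how little it costs to remove the ambiguity.

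**What to change.** Amend three places together: exclusion criterion 32 in the synopsis, non-inclusion criterion 32 in section 4.3, and the live-vaccine entry in section 6.5. They should give the same post-treatment period, define one starting event (which drug's last dose starts the clock when the two stop at different times), and say whether the rule applies to arm A, arm B or both. Section 6.5 should also either repeat the pre-treatment restriction or refer to criterion 32 for it. The sponsor must choose the period; this review does not say which one is right.

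The cost is a short wording change in each of three places, which can go into the next amendment. Because it touches safety, the sponsor should decide under section 12.6 whether it counts as substantial. No new data, analysis or patients are needed.

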7.1. IMMUNOHISTOCHEMISTRY STUDY

The expression of cyclin D1 protein will be sought by immunohistochemistry on tissue sections of paraffin-embedded specimens.

We will investigate any association between protein expression and response to treatment.

In addition, depending on the progress of knowledge at the time of the study is completed, other biomarkers predictive of response to treatment can be explored by IHC on the same tumor blocks.

Paraffin-embedded human solid tissue blocks will be sent off at room temperature at the end of the inclusions and addressed to:

[name] [name] Blood collection manager

Institut régional du cancer de Montpellier Centre de ressources biologiques [name]

[contact] – [contact] [contact]

Paraffin-embedded human solid tissue blocks will be returned to the home institution upon completion of ancillary study.

8. Discontinuation criteria/Subject withdrawal/end of study

8.1. DISCONTINUATION OF TREATMENT

Discontinuation of treatment does not represent withdrawal from the trial. As certain data on clinical events beyond treatment discontinuation are important to the study, they must be collected through the subject's last scheduled follow-up, even if the subject has discontinued treatment. Therefore, all subjects who discontinue trial treatment prior to completion of the treatment regimen will still continue to participate in the trial.

Patient may be discontinued from study treatment at any time if the patient, the Investigator, or the Sponsor feels that it is not in the patient's best interest to continue on study. The following is a list of possible reasons for early discontinuation of study treatment:

- Disease progression (unless there is reasonable evidence of clinical benefit to justify continuation on treatment – to be discussed with the Sponsor)
- In the investigator's opinion, continuation in the study treatment would be detrimental to the patient's well-being
- Protocol violation requiring discontinuation of study treatment
- Patient is not compliant with study procedures
- Patients with a β-HCG test consistent with pregnancy. Pregnancy will be reported as a serious adverse event.
- Any adverse event that cannot be adequately managed with dose modifications, including dose interruption > 28 days (unless there is reasonable evidence of clinical benefit to justify continuation on the protocol – to be discussed with the Sponsor)
- Discontinuation of treatment during more than 4 weeks
- Patient death
- New cancer
- Lost to follow-up

(The Investigators should make every effort to recontact the patient to identify the reason why he/she failed to attend the visit, and to determine the patient health status, including at least the vital status. Attempts to contact such patients must be

documented in the patient's records (e.g., times and dates of attempted telephone contact, receipt for sending a registered letter).

8.2. WITHDRAWAL FROM THE TRIAL

A subject must be withdrawn from the trial if the subject or subject's legally acceptable representative withdraws consent from the trial.

If a subject withdraws from the trial, they will no longer receive treatment or be followed at scheduled protocol visits.

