Appendix 5) must be performed if only it weren't performed at the end of

treatment visit.

(CT scan of the abdomen, pelvis and chest or hepatic MRI and CT scan of the

pelvis and chest without injection).

Tumor markers: CEA (Carcino-Embryogenic Antigen), CA 19.9 (Carbohydrate

Antigen 19-9) if not done at the EOT visit

Concomitant medications (including anti-cancer medication)

Adverse events documentation

Follow-up every other month until Death

Vital status

Anti-cancer medications

Telephone follow-up is acceptable. Site staff must use caution when contacting the patient's family for this information, especially if they are no longer under the care of the investigator,

so as to not inadvertently cause any distress to the family of a patient who is no longer alive.

6. Treatments

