9.1 Sample size

The main objective is the comparison of overall survival in the regorafenib and REGIRI combination (Regorafenib + Irinotecan) arms in mCRC patients harboring Cyclin D1 A/A genotype.

The aim is to increase the median overall survival from an estimated baseline of 7 to 15 months corresponding to 1-year OS of 30% to 57%, respectively with a HR=0.47. A total of **55 events are required** to detect this difference if it is true with 80% power and using a 2-sided log-rank test at the 5% level of significance.

A total number of required patients is 68 without drop-out.

Considering 15% additional patients lost to follow-up on estimated patients number, the sample size is 78 patients (2*39) to observe the required number of events.

Because the A/A CCND1 genotype is present in 25% of patients with metastatic colorectal cancer, 312 patients will need to be screened.

No interim analysis was planned.

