10.2.3 Pregnancy

According to the regulatory recommendations with respect to potential genotoxicity and teratogenicity (CFTG 21/09/2020, version 1.1) the durations of contraceptives for women of childbearing potential (WOCBP) and men to ensure effective contraception during treatment with regorafenib are respectively 7 months and 4 months in men sexually active with women of childbearing potential after last dose of regorafenib.

For Irinotecan, the durations of contraceptives for women of childbearing potential (WOCBP) and men are respectively 6 months and 3 months in men sexually active with women .

For female patients treated with the investigational product, the treatment with this product should be discontinued immediately at the occurrence or suspicion of occurrence of pregnancy and the patient should be withdrawn from the study (after confirmation of the pregnancy by a urine or blood test).

The pregnancy should be followed up to determine outcome, including spontaneous or voluntary termination, details of the birth, and the presence or absence of any birth defects, congenital abnormalities, or maternal and/or newborn complications.

In accordance with the recommendations for fertility preservation, the investigator may propose to the patient a protocol of conservation of ovocytes for women and of sperm cells for men.

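### Section 8.2 ends scheduled follow-up when a patient withdraws consent and does not say that vital status is kept; a cheap improvement that protects the overall survival endpoint

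*Combined protocol and SAP*

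**What the plan says.** Section 8.2 has one trigger and one consequence. The trigger: "A subject must be withdrawn from the trial if the subject or subject's legally acceptable representative withdraws consent from the trial". The consequence: "If a subject withdraws from the trial, they will no longer receive treatment or be followed at scheduled protocol visits". Vital status is not mentioned.

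Section 10.2.3 adds a second route. For a pregnant patient, after treatment is stopped, "the patient should be withdrawn from the study (after confirmation of the pregnancy by a urine or blood test". Section 8.1 lists pregnancy only among the reasons for stopping treatment.

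Other patients are covered:

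- Section 8.1, treatment stopped: "Discontinuation of treatment does not represent withdrawal from the trial". These patients stay in the trial.
- Section 8.1, lost to follow-up: the investigator tries to re-contact the patient "to determine the patient health status, including at least the vital status".
- Section 5.5: "Follow-up every other month until Death", recording vital status and anti-cancer medication. Telephone contact is accepted.

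Section 2.2.1 counts death from any cause from randomisation, and section 9.3 analyses the ITT population with a log-rank test stratified by RAS. Section 2.2.2 gives a censoring rule for PFS; no rule is given for overall survival. Section 9.3 says that a SAP will be written before database lock. Section 3.1 describes the trial as open.

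**The concern.** Sections 5.5 and 8.1 show that the sponsor wants vital status for everyone, including patients who stop treatment or miss visits. Patients who withdraw consent are the one group for whom nothing is said. If a site reads section 8.2 literally and makes no further enquiry, the patient leaves the survival analysis at the last date known alive.

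Kaplan-Meier and log-rank methods assume that censoring is unrelated to prognosis. In heavily pretreated metastatic disease a patient may well withdraw when getting worse. Because treatment is known to patient and investigator, the reasons and the frequency may differ by arm. More such withdrawals in one arm would make that arm look better than it is. A later SAP can state a censoring rule, but it cannot recover deaths that were never collected.

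**Working it through.** **1. The plan's own figures.** Two-sided 5%, 80% power, 1:1 allocation, Schoenfeld formula: events = (1.960 + 0.842)² / (0.25 × ln(HR)²). With HR = 7/15 this is 54.05, rounded up to 55, as in section 9.1. (HR rounded to 0.47 gives 55.07; 55 events then have 79.9% power.) Patients: 68 × 1.15 = 78.2, stated as 78.

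**2. Is the event count at risk?** Assume exponential survival, uniform accrual over 64 months and cut-off 5 months later (January to June 2025). The probability of an observed death is 1 − [exp(−5λ) − exp(−69λ)] / (64λ).

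- Control, λ = ln 2 / 7: 0.904
- REGIRI, λ = ln 2 / 15: 0.746
- Expected deaths: 39 × (0.904 + 0.746) = 64.3, against 55 required

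If loss is unrelated to prognosis, 5%, 10%, 15% and 20% loss leave 61.5, 58.7, 55.9 and 53.0 deaths, with 84.2%, 82.5%, 80.6% and 78.5% power at HR 0.47. Up to 15%, the count holds. What remains is possible bias.

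**3. Size of the bias, by simulation.** From the documents: 78 patients, 1:1, medians of 7 and 15 months (or 7 in both arms for no effect), 64 + 5 months, stratified two-sided log-rank test. Assumed, because the documents give nothing: the withdrawal rate; withdrawal 0 to 2 months (uniform) before the patient's own death; censoring at withdrawal; two strata without prognostic effect. Each scenario was run several times with 4,000 to 16,000 trials; ranges show the spread between runs.

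| True effect | Withdrawal | Estimated HR | Result |
|---|---|---|---|
| None | none | 1.00 | 2.7% false positives favouring REGIRI |
| None | REGIRI only, 5% | 0.95 | about 4% |
| None | REGIRI only, 10% | 0.90 to 0.91 | about 6% |
| None | REGIRI only, 15% | 0.86 to 0.87 | 8 to 9% |
| None | both arms, 15% | 1.00 | 2.6 to 2.7% |
| 7 vs 15 months | none | 0.46 | power 84% |
| 7 vs 15 months | control only, 5% | 0.48 | power 75 to 78% |
| 7 vs 15 months | control only, 15% | 0.52 to 0.54 | power about 62% |
| 7 vs 15 months | both arms, 5% | 0.46 | power 82 to 83% |
| 7 vs 15 months | both arms, 15% | 0.46 | power 77 to 78% |

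**4. A different withdrawal model.** Here patients are censored at 30 to 90% of their own survival time, about 14% are withdrawn overall, and the test is unstratified. With no true effect, 25% control / 5% REGIRI gives HR 1.17, and 5% / 25% gives 0.85; two-sided type I error rises from about 5% to 9–10%. With a true HR of 0.467, the same splits give HR 0.54 (power 59%) and 0.39 (power 93%). Equal withdrawal of 15% gives HR 0.45 and power 81%. The pattern is the same: imbalance between arms drives the bias.

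**The case against.** Several stronger readings are tempting, and the documents do not support them.

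- *Patients who refuse only treatment or visits are censored for survival.* Section 8.1 keeps patients who stop treatment in the trial, and section 5.5 accepts telephone contact, so declining visits alone need not end survival follow-up. The gap concerns withdrawal of trial consent, and pregnancy under section 10.2.3.
- *The plan expects 15% of patients to be missing in this way.* Section 9.1 says "Considering 15% additional patients lost to follow-up on estimated patients number". That is loss to follow-up, for which section 8.1 already seeks vital status. It is not a consent-withdrawal rate.
- *Section 8.2 forbids collecting vital status.* It ends treatment and scheduled visits and is otherwise silent. Censoring at withdrawal is an inference from that silence and from the missing survival censoring rule.
- *The patient is never asked.* The consent pages are not in the copy reviewed, so their wording cannot be counted as missing. Section 12.3 also gives patients a right to oppose transmission of their data, which any change must respect.
- *The trial will fall short of 55 deaths.* Step 2 shows that the inflation to 78 covers 15% non-informative loss.

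It is also fair to say that the largest figures come from extreme cases: 15% withdrawal in one arm, none in the other, all close to death. At 5% the effect is modest, and with equal rates the hazard ratio hardly moves.

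All of this stands, and it narrows the point. It does not supply the missing instruction for patients who withdraw consent.

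**Conclusion.** The point holds as a cheap improvement. For consent withdrawal, and for pregnancy under section 10.2.3, the visible plan ends scheduled follow-up without saying that vital status is kept. Following it literally can lose primary-endpoint deaths for good.

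The harm is conditional on two unknowns, the withdrawal rate and its imbalance between arms. It ranges from almost no bias (equal rates, with power of 77 to 83% instead of 84%) to roughly a threefold rise in false positives favouring REGIRI (15% in that arm only). These figures rest on exponential survival, uniform accrual and withdrawal shortly before death. A reader might infer that the primary test is already compromised; the documents do not show that.

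**What to change.** 1. In section 8.2, record the scope of each withdrawal: visits and contacts, or all further data collection.
2. State there that, unless the patient objects to further data collection, vital status continues to be collected at the two-monthly contact or from the medical file.
3. At the overall survival cut-off, seek vital status for every randomised patient not known to have died who has not objected.
4. Reconcile section 10.2.3 with section 8.1 on whether pregnancy ends trial participation or only treatment.
5. Confirm that the consent form already allows this, or add a line.

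The cost is a wording change and minor site work: some calls or file checks. Patients who refuse all use of their data would still be lost, as they must be.
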